Précis:	We will conduct a feasibility study to develop and assess procedures for improved COVID-19 triage and testing in dental practices to increase safety and perceptions of safety of Dental Health Care Workers (DHCWs) and their patients. Four National Dental Practice-Based Research Network (PBRN) member dentists and their office staff will be recruited to participate as either as a Point of Care (POC) Office or a LAB office based upon preference of the PBRN member dentist. In the POC offices, we will test out procedures for POC/SARS-CoV-2 antigen testing in DHCWs and patients of the practice along with enhanced triage using pulse oximeters. In the LAB offices, DHCWs and patients will test procedures for a saliva-based laboratory SARS-CoV-2 viral test (LAB) along with enhanced triage methods. Based on office recruitment (POC or LAB), viral, antigen and/or antibody COVID-19 tests will be administered to DCHW and patients entering the dental office. In addition, the use of pulse oximeters will be added to the DHCW and patient triage protocol. The feasibility of implementing COVID-related testing and enhanced triage procedures in the dental setting will provide preliminary data to inform a larger network-wide study grant application.
Objectives:	Primary: The primary objective of this study is to assess the feasibility of procedures for both COVID-19 point-of-care and lab-based testing along with enhanced triage in dental offices.
Population:	This study will take place in dental offices, each of which with at least one National Dental PBRN member dentist. DHCWs working in a dental office with a participating National Dental PBRN dentist and their adult patients 18 years old and older will be recruited to participate. In each office, up to 10 DHCWs (dentists, hygienists, assistants and office staff) including the PBRN member dentists and up to twenty (20) patients will be enrolled. In total, up to forty (40) DHCW (dentists, hygienists, assistants and office staff will be enrolled) and eighty (80) patients enrolled.
Number of Sites:	Four (4) National Dental PBRN offices
Study Duration:	Twelve (12) months
Subject Participation Duration:	DHCWs in both POC offices and LAB offices will participate in the study for 1 month. Patients being seen in POC or LAB offices will participate in the study for approximately two (2) weeks.
Estimated Time to Complete Enrollment:	Six (6) months

Schematic of Study Design

2 INTRODUCTION: BACKGROUND INFORMATION AND SCIENTIFIC RATIONALE

2.1 Background Information

Description of Problem:

The COVID-19 pandemic: COVID-19 has created serious concerns about the safety of patients and dental professionals as they return to a practice environment. The spread of this ubiquitous virus was first thought to be through droplets but soon it became clear that the virus could be spread by aerosols [5,6]. Many dental procedures require the mechanical preparation of hard and soft tissue using high speed handpieces which are water cooled and generate significant aerosolized sprays. The extent to which dentally-generated aerosols linger within operatories has not been clearly tested but it is certain that clinic dental personnel will be exposed to significant aerosol sprays derived from patients' oral cavities [7]. As we learn more about COVID-19 and viral transmission we understand that infection and spread of the virus is due to the viral load (or dose) and the time of contact [8,9].

Uniqueness of Dental Practice: Unlike many procedures in medicine, dental/patient contact is eye to eye with close proximity between patient and dental professionals [10]. Furthermore, a dental procedure can often take as long as 1 hour and prolonged close contact between dentist and patient is inevitable. Despite personal protective equipment (PPE) that includes N95 masks, face shields, gowns, and high-speed suction, viral spread from infected patients is likely in the dental setting. This suggests that the only safe solution for maintaining the health and safety of dental professionals in the time of COVID-19 is removing virus-infected patients from their offices [11].

Waiting Rooms and Airflow: Obvious issues confronting dental practices have been discussed, however, waiting rooms with patients, bathrooms and passageways are all additional areas within offices that can be of safety concern. Further, the airflow in confined office spaces where patients can be waiting for 30 minutes or more can be hazardous if an asymptomatic but COVID-19 infected patient is in close proximity to a susceptible patient. Patients in a dental office can be at risk for infection that can have varied presentation and severity and may be life threatening especially in patients with pre-existing conditions [21-23].

Solutions: One way of providing the security that dental offices are safe for both the dental professional and patient is by taking measures to prevent anyone who harbors the COVID-19 virus from entering the office. This of course would necessitate testing every patient at every visit or by establishing the fact that patients are safe if they have neutralizing antibody to the COVID-19 virus. These solutions, at this moment, appear to be impractical particularly if the virus affects a very small percentage of the population, testing is inaccurate, and obtaining testing results is not immediate. A solution to this problem is imperative both for the safety and security of the patient and dental professional. But what's to be done? How do we achieve our goal of providing a safe and secure environment that allows for routine dental care?

Several challenges exist to routine and comprehensive testing: The costs, turnaround time (maximum practical utility would perhaps be derived from a simple, rapid, accurate, inexpensive point-of-care test that is not technically demanding, and such a test has not yet been validated). This proposal compares the use of one such candidate POC test with the current screening gold-standard.

Conclusions: With each day, patients are not receiving dental services because of a COVID-19 transmission concern. Understanding risk associated with COVID-19 transmission in a dental practice and the effective use of testing and other practice modifications could dramatically reduce the risk, facilitating dental health care providers and patients to be comfortable with seeking/providing essential dental services. This proposal is designed to develop procedures that address this serious problem and test the feasibility of these procedures in a pragmatic manner to address this existing insurmountable problem that can affect the future of dental practice and the dental health we have come to expect.

2.2 Rationale

Typical dental protocols recommend twice yearly visits to dentists for prevention and maintenance of oral health [12,13]. Dental patients who may be asymptomatic for medical conditions are seen routinely in dental offices and can be screened for the early phases of medical disease during routine dental visits. For example, blood pressure monitoring and simple blood test for glycosylated hemoglobin (HbA1c) levels can be performed in dental offices, with referral to medical personnel for further assessment [18,19]. This medical screening can be considered as value-added should dental health professionals provide augmented diagnostic benefit to patients who are unaware of their need for medical intervention. However, in this time of uncertainty dentistry has been impacted by fear and poorly defined strategies to mitigate COVID-19, that can compromise the willingness of dental professionals to open their dental practices [20].

Little is Known Regarding the Effectiveness COVID-19 Triage in Dental Practice: Little is known about the effectiveness of triage protocols which have been recommended by the CDC. For example, most offices are using temporal thermometers, yet many are uncalibrated. In addition, screening questions continue to evolve, and the veracity of patient responses remains unverified.

Little is Known Regarding the Impact of COVID-19 Testing in Dental Practice: Little is known about the value of testing and about the willingness of dental health care workers (DHCW) to implement COVID-19 testing in a dental office, who would pay for the testing, or the most effective use of such testing.

The following questions need to be answered:

- Perception of safety and comfort: Will patients and DHCW in an office with either LAB or POC testing feel safer and be more comfortable delivering/receiving care during a COVID-19 or other infectious disease pandemic?
- Testing preference: Do DHCW and patients prefer POC testing rather than testing that requires laboratory processing?
- Effectiveness of triage: Is the triage protocol being followed today effective or do patients and DHCW respond negatively to COVID-19 symptoms because of the fear of not being seen or being turned away from work?
- Effectiveness of triage methods: Are objective measures such as temperature and pulse oximeter readings effective in identifying “asymptomatic” cases?

2.2.1 Potential Risks

This research involves testing procedures with varying degrees of risk to the study participants.

- Saliva Test- minimal risk. The saliva test is non-invasive, requires spitting into a tube, and is completed independently, without interaction with a member of the healthcare team.
- Nasal swab- minimal risk. The nasal swab involves insertion of a swab into the forward part of the nasal cavity (not beyond the nares) by a member of the healthcare team which may cause slight discomfort to the participant.
- Tongue swab – minimal risk. The tongue swab involves rolling a small circular brush on the tongue to collect epithelial cells which may cause slight discomfort to the participant.
- Finger prick- minimal risk. A finger prick test is a procedure in which a finger is pricked with a lancet to obtain a small quantity of capillary blood for testing. The site where the blood is to be collected is sterilized with a topical germicide, and the skin is pierced with a sterile lancet. There is a slight risk of discomfort from the lancet stick and irritation or infection in the area where the lancet punctures the skin.

In addition, different COVID-19 test types have varying degrees of sensitivity and specificity, which may result in false negative and false positive test results. A false negative result may give a participant a false sense of security, and the patient would have been treated with each office's infection control protocol

regardless of participation in the study. Regardless, false negative test results may pose additional viral transmission risk to DHCW who interact with and treat the patient, and other individuals who come into contact with the asymptomatic but infected patient. On the other hand, a false positive result will prompt the DHCW or patient to undergo additional testing by their primary health care provider and may cause additional anxiety. Should they test positive again, they would need to follow their local health department recommendations which may require quarantine.

There is a risk of loss of confidentiality for all study participants. Precautions will be in place to minimize this risk, such as collecting only minimal identifying information, using unique study codes for participants, collecting data using encrypted computers, and maintaining electronic data files on a password-protected computer drive, and storing data on encrypted computers or in locked cabinets (located in locked offices). Individual identifier numbers that are linked to participant contact information will be stored separately from the data. Compliance with all IRB regulations concerning data collection, data analysis, data storage, and data destruction will be strictly observed.

2.2.2 Potential Benefits

There is no benefit to DHCW and patients participating in this study beyond the fact that DHCW and patients would receive the results of the COVID-19 tests they undergo.

3 OBJECTIVES AND OUTCOME MEASURES

3.0 Feasibility Study Outcomes

Objectives	Brief Description/Justification of Outcome Measure	Outcome Measured By	Time Frame
To Determine DHCW and Patient Willingness to Participate	Willingness to participate is important in determining whether dental offices, DHCW and patients would be willing to participate in a large-scale study	
 Ratio of DHCW agreeing to participate as compared to all DHCW asked to participate Ratio of patients agreeing to participate as compared to all patients asked to participate Thoroughness of consent process and ability to ask questions 	
Willingness to Participate:
 
 DHCW – at time of consent by DHCW consent Patients – at time of consent by patients
To Determine DHCW and Patient Willingness/Ability to Follow Thru with Triage, Testing and Survey Administration Procedures	Determining willingness and ability to follow thru with triage, testing and survey administration procedures is important for refining the survey procedures	
For both DHCW and Patients
 
 % who complete the study % who complete surveys 
 Start-of-Study DHCW Survey End-Of-Study DHCW Survey Pre-Visit Patient Survey End-of-Visit Patient Survey % activities occurring within the defined window 
 Consents Start-of-Study DHCW Survey, Triage and Testing End-Of-Study DHCW Survey, Triage and Testing Mid-Study Triage Testing Pre-Visit Patient Survey End-of-Visit Patient Survey Patient Testing % who feel testing (Saliva, PCR, POC, and ELISA Antibody) procedure was easy to comply with 
 Specimen collection Specimen preparation for shipping Specimen storage Timeliness of results Reporting of results 	
% Complete Study:
 
 For DHCW - At time End-of-Study (Day 28) Patients – End-Of-Visit (Day 1) 
% All Surveys Completed:
 
 For DHCW - At time End-of-Study (Day 28) Patients – End-Of-Visit (Day 1) 
% Activities Occurring within the defined window:
 
 For DHCW – Consent, Start-of-Study Visit, Mid-Visit, End-of-Study Visit Patients – Consent, LAB material receipt, LAB specimen sent to laboratory, LAB results, Treatment Visit 
% Feel Testing Protocol was Easy to Comply With:
 
 For DHCW - At time End-of-Study (Day 28) Patients – End-Of-Visit (Day 1)

Objectives	Brief Description/Justification of Outcome Measure	Outcome Measured By	Time Frame

To Determine Ease of Use with REDCap Survey Instruments
 
 • Dental Health Care Worker Subject 
 ◦ Start-of-Study Survey ◦ End-of-Study Survey ◦ Triage Survey • Patient Subject 
 ◦ Start-of-Visit Survey ◦ End-of-Visit Survey ◦ Triage Survey 	Determining the ease of use and completeness of the REDCap instruments enables refinement of the system	
For both DHCW and Patients
 
 • % who feel surveys are easy to complete due to administration method: 
 ◦ Start-of-Study DHCW Survey ◦ End-of-Study DHCW Survey ◦ Pre-Visit Patient Survey ◦ End-of-Visit Patient Survey ◦ Triage Case Report • % who feel survey questions were understandable: 
 ◦ Start-of-Study DHCW Survey ◦ End-of-Study DHCW Survey ◦ Pre-Visit Patient Survey ◦ End-of-Visit Patient Survey ◦ Triage Case Report • % completed surveys: 
 ◦ Start-of-Study DHCW Survey ◦ End-of-Study DHCW Survey ◦ Pre-Visit Patient Survey ◦ End-of-Visit Patient Survey ◦ Triage Case Report 	
% indicating surveys were easy to complete due to administration method:
 
 • For DHCW - At time End-of-Study (Day 28) • Patients – End-Of-Visit (Day 1) 
% indicating survey questions were easy to understand:
 
 • For DHCW - At time End-of-Study (Day 28) • Patients – End-Of-Visit (Day 1) 
% Surveys Completed:
 
 • For DHCW - At time End-of-Study (Day 28) • Patients – End-Of-Visit (Day 1)

3.1 Primary Outcomes for Full Study (Data Collection is Being Performed to Determine Instrument Feasibility)

Full Study Objective	Brief Description/Justification of Outcome Measure	Outcome Measured By	Time Frame
Objective 1 – Dental health care personnel feel safe in the dental office	
Safety Culture Evaluation Survey for DHCW is a 6-item survey using a 4 point Likert scale seeking the agreement with 6 criteria associated high performing safety organization characteristics.
 
Willingness to Come to Work reflects a DHCW's safety in the workplace.
 
Willingness to Refer Other Patients reflects DHCW's safety of the dental practice.
	
DHCW - Safety Culture Evaluation Survey: 6 item survey. Numeric responses to each item using a four-point Likert Scale are summed for a score which reflects the level of safety in the organization. (1=strongly agree, 2=agree, 3=disagree, 4=strongly disagree.)
 
DHCW- Safety: How safe to do feel coming to work? 5 Point Likert scale
 
DHCW Willingness to Refer Other Patients: How likely would you refer a family or friend to this dental office? 5 Point Likert Scale
	
Sense of Safety for Dental Health Personnel:
 
 • Start of study • End of study 
Willingness to Refer Other Patients:
 
 • DHCW – Start of study • DHCW – End of study

3.2 Secondary Outcomes for Full Study (Data Collection is Being Performed to Determine Instrument Feasibility)

Objective	Brief Description/ Justification of Outcome Measure	Outcome Measured By	Time Frame
Objective 2: Determine the Efficiency and Effectiveness of: 
 • Efficiency of DHCW Triage Protocols • Efficiency of Patient Triage Protocols • Effectiveness Patient Testing Protocols 	
Efficiency of Triage Protocols:
 
 • Acceptability of triage protocols is based upon resources (time and effort and facilities) required to implement the protocol 
Effectiveness of Triage Protocols
 
 • Dentist's willingness to continue use of triage protocols is based upon the usefulness/outcomes of the triage. 
Efficiency of Testing Protocols:
 
 • Acceptability of testing protocols is based upon resources (time and effort and facilities) required to implement the protocol 
Effectiveness of Testing Protocols
 
 • Dentist's willingness to implement testing protocols is likely to be based upon testing's ability to identify asymptomatic DHCW and patients. 	
Efficiency of Triage Protocols:
 
 • Time needed to complete triage survey 
Effectiveness of Triage Protocols
 
 • Comparison of number of DHCW not able to report to work due to LAB or POC test results • Comparison of Triage Survey to Medical History consistent with COVID-19 symptoms for DHCW 
Efficiency of Testing Protocols:
 
 • Time and supplies needed to conduct LAB vs. POC test 
Effectiveness of Testing Protocols
 
 • Comparison of number of DHCW not able to report to work • Comparison of number of patients not able to report for their patient visits 	
Efficiency of Triage Protocols:
 
 • End of study 
Effectiveness of Triage Protocols
 
 • End of study 
Effectiveness of Testing Protocols:
 
 • End-of-Study 
Effectiveness of Testing Protocols
 
 • End-of-Study

3.3 Tertiary/Exploratory Outcomes for Full Study (Data Collection is Being Performed to Determine Instrument Feasibility)

Objective	Brief Description/Justification of Outcome Measure	Outcome Measured By	Time Frame
Objective 3 (exploratory): Examine SARS-CoV-2 Positivity Rate and Immuno-Conversion Rate 
 • DHCW positivity rate • DHCWs with IgG • DHCWs with IgM • DHCWs who immune-convert 	
Positivity Rate:
 
 • POC antigen with a nasal swab • PCR with a saliva or tongue scraping specimen 
Immuno-conversion Rate
 
 • ELISA with Capillary Blood specimen 	
DHCW Positivity Rate:
 
 • POC antigen • PCR viral test 
DHCW Immuno-conversion Rate
 
 • ELISA antibody 	
DHCW Positivity Rate:
 
 • Start of Study • Every 2 weeks • End of Study 
DHCW Immuno-conversion Rate
 
 • Start-of-Study • Every 2 Weeks • End-of-Study

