6 STUDY SCHEDULE

6.1 Dental Health Care Worker Subjects

The following is the schedule of events for Dental Health Care Worker Subjects in the POC Offices.

Visit	Day	Dental Health Care Worker Subjects Activities Performed
Enrollment (15 minutes)	Day -28 (+/- 29 days)	
 • Obtain written Informed Consent
Start-of-Study (35 minutes)	Day 0	
 • Complete Start-of-Study Survey • Complete Start-of-Study Triage Case Report • Undergo POC (antigen) COVID-19 test • Provide specimen for ELISA (antibody) test
Mid-Study (20 minutes)	Day 14 (+/- 7 days)	
 • Complete Mid-Study Triage Case Report • Undergo POC Covid-19 Test
End-of-Study (40 minutes)	Day 28 (+/- 14 days)	
 • Complete End-of-Study Triage Case Report • Undergo POC COVID-19 Test • Provide specimen for ELISA (antibody) test • Complete End-of-Study Survey • Complete DHCW Participation Questionnaire

The following is the schedule of events for Dental Health Care Worker Subjects in the LAB Offices.

Visit	Day	Dental Health Care Worker Subjects Activities Performed
Enrollment (15 minutes)	Day -28 (+/- 29 days)	
 • Obtain written Informed Consent
Start-of-Study (35 minutes)	Day 0	
 • Complete Start-of-Study Survey • Complete Start-of-Study Triage Case Report • Provide specimen(s) for PCR (viral) test • Provide specimen for ELISA (antibody) test
Mid-Study (20 minutes)	Day 14 (+/- 7 days)	
 • Complete Mid-Study Triage Case Report • Undergo POC Covid-19 Test
End-of-Study (40 minutes)	Day 28 (+/- 14 days)	
 • Complete End-of-Study Triage Case Report • Provide specimen(s) for PCR (viral) test • Provide specimen for ELISA (antibody) test • Complete End-of-Study Survey • Complete DHCW Participation Questionnaire

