 - A small lancet will create a finger prick to collect a small blood sample for collection using a Mitra cartridge (blood specimen collection device)

- The Mitra cartridge will be packaged by the DHCW and placed in the practice collection box to await shipment to Rutgers
- The sample will be processed by the Public Health Research Institute (PHRI) Lab at Rutgers

Mid-Study- Day 14 (+/- 7 days)

- Undergo a COVID-19 triage screening in the office*
- Complete a SARS-CoV-2 POC test** (administered by the PBRN practitioner or designated investigator)
 - A nasal swab will sweep the inside of the participant's nose (not beyond the nares) to collect your specimen for the SARS-CoV-2 test
 - The office staff will process the specimen

[figure not shown]
End of Study- Day 28 (+/- 7 days)

- Undergo a three-part COVID-19 triage screening*
 - Symptom questions
 - Temperature check
 - Pulse oximeter reading
- Complete two SARS-CoV-2 tests**
 - SARS-CoV-2 POC test (administered by PBRN practitioner or designated investigator)
 - A nasal swab will be swept inside the participant's nose (not beyond the nares) to collect the specimen for the SARS-CoV-2 test
 - The office staff will process the specimen in the dental office
 - ELISA Antibody test (specimen collected by the PBRN practitioner, designated investigator or self)
 - A small lancet will create a finger prick to collect a small blood sample for collection using a Mitra cartridge (blood specimen collection device)
 - The Mitra cartridge will be packaged by the DHCW and placed in the practice collection box to await shipment to Rutgers
 - The sample will be processed by the Public Health Research Institute (PHRI) Lab at Rutgers
- Complete two electronic surveys:
 - *DHCW End of Study Survey*- Questions include importance of triage and testing, importance of PPE measures, perceptions of safety and comfort in the workplace, safety culture in the office, SARS-CoV-2 testing preferences, dentists' role in SARS-CoV-2 testing, willingness to test in the office, and vaccinations
 - *DHCW Participation Survey*- Questions explore perceptions related to study participation including survey and testing logistics

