 - Questions include demographics, PPE used in the office, work practice controls used in the office, importance of triage and testing, importance of PPE measures, perceptions of safety and comfort in the workplace, safety culture in the office, SARS-CoV-2 testing preferences, dentists' role in SARS-CoV-2 testing, and willingness to test in the office
- Undergo a three-part COVID-19 triage screening*
 - Symptom questions
 - Presence or absence of:
 - fever or chills
 - cough
 - shortness of breath or difficulty breathing
 - fatigue
 - muscle and body aches
 - headache
 - loss of taste

- loss of smell
- sore throat
- congestion or runny nose
- nausea or vomiting
- diarrhea
- Temperature check
- Pulse oximeter reading
- Complete two COVID-19 related tests**
 - SARS-CoV-2 PCR viral test
 - Saliva (self-collected) and tongue specimens (collected by PBRN practitioner, designated investigator or self)
 - ELISA Antibody test (specimen collected by PBRN practitioner, designated investigator or self)
 - A small lancet will create a finger prick to collect a small blood sample for collection using a Mitra cartridge (blood specimen collection device)
 - The Mitra cartridge will be packaged by the DHCW and placed in the practice collection box to await shipment to Rutgers
 - The sample will be processed by the Public Health Research Institute (PHRI) Lab at Rutgers

Mid-Study- Day 14 (+/- 7 days)

- Undergo a COVID-19 triage screening in the office*
- Complete a SARS-CoV-2 PCR Viral test**
 - Saliva (self-collected)

[figure not shown]
End of Study- Day 28 (+/- 7 days)

- Undergo a three-part COVID-19 triage screening*
 - Symptom questions
 - Temperature check
 - Pulse oximeter reading
- Complete two SARS-CoV-2 tests**
 - SARS-CoV-2 PCR viral test
 - Saliva (self-collected) and tongue specimens (collected by PBRN practitioner, designated investigator or self)
 - ELISA Antibody test (specimen collected by PBRN practitioner, designated investigator or self)
 - A small lancet will create a finger prick to collect a small blood sample for collection using a Mitra cartridge (blood specimen collection device)
 - The Mitra cartridge will be packaged by the DHCW and placed in the practice collection box to await shipment to Rutgers
 - The sample will be processed by the Public Health Research Institute (PHRI) Lab at Rutgers
- Complete two electronic surveys:

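### DHCW conversion is promised every two weeks but ELISA blood is drawn only at start and end, PCR specimens differ by visit, and no rule separates vaccine response from infection

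*Combined protocol and SAP*

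**What the plan says.** **Outcome.** Objective 3 in Section 3.3 covers DHCW positivity, IgG, IgM and "DHCWs who immune-convert". Positivity and conversion share one time frame: start, every two weeks, end. For LAB offices, positivity is "PCR with a saliva or tongue scraping specimen". The section heading marks these as full-study outcomes, collected here to test the instruments.

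**ELISA schedule.** Both DHCW tables in Section 6.1 list "Provide specimen for ELISA (antibody) test" at Start-of-Study and End-of-Study and not at Mid-Study. The Section 7 procedures for Groups 1 and 3 do the same.

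**PCR schedule, LAB DHCWs.** Section 7 (Group 3) asks for "Saliva (self-collected) and tongue specimens (collected by PBRN practitioner, designated investigator or self" at Day 1 and at the end. At mid-study it says "Complete a SARS-CoV-2 PCR Viral test" and lists saliva only. The LAB table in Section 6.1 gives the mid-study test as "Undergo POC Covid-19 Test". Appendix A1 marks PCR twice.

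**Assay and vaccination.** Section 7.2.1 describes the ELISA as a quantitative IgG and IgM test, with no target antigen and no cut-off. Vaccination is named as a topic at the end of the End of Study Survey ("willingness to test in the office, and vaccinations"), and Section 7.1 lists opinions on vaccination at the start. No item for vaccination status or dose date is shown. Section 5.2 excludes only people who took part in the previous Rutgers feasibility study.

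**The concern.** Three things stand between the outcome as named and a rate that can be interpreted.

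- A two-weekly conversion rate needs a mid-study blood sample, and no itemised schedule has one.
- If a positive result on either specimen counts, PCR positivity can change between visits only because the number of specimens changes.
- Nobody is excluded for vaccination or seropositivity and the assay target is unstated, so a DHCW vaccinated between draws might turn positive without infection. The data shown would not allow that to be recognised.

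The study is meant to refine instruments and may inform a larger network-wide application. An outcome whose time frame cannot be met, and whose key covariate is not collected, is a fault it should remove. Dose dates not asked for during the study may not be recoverable later.

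**Working it through.** The plan gives no expected rate, sample size or test for this outcome, so there is no figure to reproduce. The first two steps compare sections; the rest are illustrations on stated assumptions.

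**1. Conversion times.** Section 3.3 implies samples at Days 0, 14 and 28: 3 samples, hence 3 − 1 = 2 intervals. Sections 6.1 and 7 give 2 samples, hence 2 − 1 = 1 interval per DHCW. Appendix A1 agrees in number, with two ELISA marks against three for the antigen test; its column alignment is not readable in the text available, so only the counts are used.

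**2. PCR specimens per LAB DHCW.**

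| Source | Start | Mid | End |
|---|---|---|---|
| Section 7, Group 3 | 2 | 1 | 2 |
| Section 6.1, LAB table | specimen(s) | 0 (POC test) | specimen(s) |

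Sections 5.3 and 7.2.1 say saliva and/or tongue. No rule combines the two specimens or settles discordant results.

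**3. Effect of a second specimen.** Assume saliva sensitivity a = 0.6 to 0.9, tongue sensitivity b = 0.4 to 0.8, independence, and that either positive counts.

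- Detection with both is 1 − (1 − a)(1 − b), from 0.76 (0.6, 0.4) to 0.98 (0.9, 0.8). With saliva alone it is 0.60 to 0.90.
- The gap is (1 − a)b. The smallest is 0.1 × 0.4 = 0.04, or 0.04/0.94 = 4% in relative terms. The largest is 0.4 × 0.8 = 0.32, or 0.32/0.92 = 35%.
- LAB DHCWs number at most 2 × 10 = 20. At an assumed 5% prevalence, 20 × 0.05 = 1 is infected, so the gap is 0.04 to 0.32 of a person.
- At an assumed specificity of 0.99, false positives are 1 − 0.99² = 2.0% with two specimens and 1.0% with one.

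**4. Choice of denominator.** Assume 40 DHCWs, of whom 5% of those seronegative at Day 0 convert through infection.

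| Seropositive at Day 0 | Seronegative n | Rate over seronegatives | Rate over all 40 |
|---|---|---|---|
| 20% | 32 | 5.0% | 1.6/40 = 4.0% |
| 50% | 20 | 5.0% | 1.0/40 = 2.5% |
| 80% | 8 | 5.0% | 0.4/40 = 1.0% |

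Precision is poor either way. The exact 95% interval for 1/40 is 0.1% to 13.2%; for 1/8 it is 0.3% to 52.7%.

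**5. Can the vaccine effect be sized?** Suppose a fraction v of seronegatives is vaccinated between draws, all of them turn positive on this assay, and a fraction i of the rest convert through infection. The vaccine share of conversions is v/(v + (1 − v)i).

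- v = 10%, i = 2%: 0.10/(0.10 + 0.018) = 85%
- v = 10%, i = 5%: 0.10/(0.10 + 0.045) = 69%
- v = 5%, i = 5%: 0.05/(0.05 + 0.0475) = 51%
- v = 5%, i = 10%: 0.05/(0.05 + 0.095) = 34%
- v = 30%, i = 2%: 0.30/(0.30 + 0.014) = 96%
- Assay blind to vaccine antibody: 0%

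The documents supply neither v nor i nor the assay target, so none of these is an estimate for this study.

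**The case against.** The strongest reply is that this outcome barely matters here. Section 3.3 is headed as full-study outcomes, so the two-weekly time frame may belong to the later study. Section 11.1 plans frequencies only, lists neither positivity nor conversion, and takes only completeness from the Testing Case Report. No threshold or decision uses these rates. All of that stands and sets the priority. It does not remove the mismatch: the table describes data collected in this study, and no itemised schedule here supports its time frame. The Section 7.1 tables do list Testing Case Reports at Days 0, 14 and 28, but they do not separate ELISA from the other tests and so do not establish a mid-study draw.

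A reader might go further and infer that the rate would count vaccine responses as conversions, over DHCWs already seropositive at entry. The documents do not support that. They state no numerator rule, denominator or assay target. To convert ordinarily means to go from negative to positive, and a Day 0 ELISA exists, so a baseline-negative denominator can be formed. The gap is that it is not specified.

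A reader might also expect an artificial dip in PCR positivity at Day 14. That takes the Section 7 saliva test as settled when Section 6.1 lists a POC test, and it assumes an either-positive rule that is not stated. Positive correlation between two oral specimens from one person would shrink the gap further.

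**Conclusion.** The point holds in a limited form. On the documents alone, the two-weekly conversion time frame has no mid-study blood sample behind it. The LAB DHCW specimens differ by visit in Section 7, and Sections 6.1 and 7 and Appendix A1 do not agree on the mid-study test. Conversion is undefined, and the plan has no rule, and no dose date, with which to separate vaccine response from infection.

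The size of any vaccine bias cannot be stated. Figures such as 85% depend wholly on assumed vaccination and infection rates and on an assay that detects vaccine antibody; the bias is nil if it does not. The specimen effect is below one person under the assumptions above. Because the outcome is exploratory, labelled for the full study and tied to no decision, this is a desirable low-priority correction and no threat to the feasibility conclusions.

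**What to change.** - **ELISA times.** Restate the conversion time frame in Section 3.3 as Day 0 and Day 28, matching the itemised draws.
- **LAB mid-study test.** Reconcile Section 6.1, Section 7 (Group 3) and Appendix A1.
- **PCR positivity.** Compare visits on saliva alone, at those visits where saliva PCR is actually collected. Report tongue results separately.
- **Conversion.** Define it as ELISA-negative at Day 0 and positive at Day 28, among DHCWs negative at Day 0 with both samples. Because the assay is quantitative for IgG and IgM, fix the cut-off and the isotype rule in advance, and state the target antigen.
- **Vaccination.** Add vaccination status and dose date to the End-of-Study Survey, and report conversion separately for DHCWs with and without a dose between the two draws.

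The cost is wording and one added survey item on vaccination, with no new visit or specimen. The denominator becomes smaller, for example 20 instead of 40 if half are seropositive at Day 0, so the rate should be shown as a count with an exact interval.
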